8.1.2. Giardiasis Group

The primary endpoint for the giardiasis group is clearance of Giardiasis by day 5, defined as no detections of cysts or trophozoites of Giardia or negative antigen detection on day 5. This endpoint is analogous to the amebiasis endpoint except for the time point, and analogous methods will be applied. [Table 19](#) and [Table 21](#) will present the numbers and proportions (with 95% confidence intervals) of subjects with parasitological response by Day 7 for the treatment and placebo arms in the giardiasis strata for the asymptomatic and symptomatic populations, respective. These tables also present the difference in proportions between treatment and placebo groups and odds ratios, with their 95% confidence intervals. Separate versions of the tables will be provided for the modified-Intention-to-Treat population and the Per-Protocol population.

In the symptomatic population, the primary outcome is resolution of diarrhea by Day 5. This variable will be analyzed with the same approach above described for the analysis of parasitological response.

8.2. Secondary Efficacy Analyses

8.2.1. Amebiasis Group

[figure not shown]
The secondary outcome measures for the asymptomatic amebiasis group are:

1. Parasitological response (no detection of cysts or trophozoites on microscopic exam or negative antigen detection) by Day 3 and 5
2. Rate of decrease of trophozoite/cyst load by qPCR in stools by Days 3,5 and 7
3. Proportion of subjects with negative stool antigen test by Days 3, 5, 7, and 14
4. Proportion of subjects with sustained cure (no detection of cysts or trophozoites by microscopic exam or negative antigen detection) at 14 and 28 days
5. Proportion of subjects with relapse (same strain) or re-infection (new strain) with positive stools at 14 and 28 days by genotyping the initial vs. subsequent strain.

Secondary outcome (1) corresponds to the primary outcome, except that the time points of measurement differ. Therefore, methods perfectly analogous to those used for the primary outcome will be applied to the first secondary outcome. Secondary outcomes (3) – (5) above are also dichotomous, so will be analyzed with methods analogous to those described for the primary outcome (e.g. odds ratios with 95% confidence intervals, and/or logistic regression with confounders included as predictors).

Secondary aim (2) includes the sole numeric outcome (parasite load), and this is measured at multiple time points. For secondary aim (2), a mixed effects model will be used to compare the rate of change in parasite loads between the two study arms. A mixed effects model allows us to incorporate information for multiple time points into a single model while explicitly adjusting for the correlation (due to repeated measures on the same subjects) that naturally arises from this data structure. [4] Below the mixed effects model for the per-protocol analysis is described. This is followed by a description of how the model will be adjusted in the m-ITT population analysis in order to account for missing data.

Parasite load measured on study days 1, 3, 5, and 7 will be included in the mixed effects model. The mean parasite load with 95% confidence intervals will be displayed graphically for each time point for each treatment group, as shown in the example figure below:

If a linear relationship between parasite load and time is observed for both groups, then a model that makes use of this simplifying assumption will be used. Letting Y denote parasite load, t denote the time point (study day), and i be a subject index, and letting $treatment=1$ for those in the treatment group and $treatment=0$ for those in the placebo group, we will model parasite load as:

$$Y_{it} = \beta_0 + \beta_1 t + \mu_i + \alpha_i t + \beta_2 treatment + \beta_3 treatment \cdot t + \epsilon,$$

Note that the above graph does not depict a linear decline in parasite load over time. If the relationship is nonlinear, as depicted in the figure above, then transformation (e.g. log transformation) may be applied, or we will fit the following model, which relaxes the linearity assumption. Let $1_{[t=k]}$ denote an indicator variable taking the value one when $t=k$ and zero otherwise. Let u_i denote the random intercept for subject i , and let α_i denote the random slope for subject i , and assume these random effects are normally distributed with mean zero. Then without assuming linearity, the parasite load for subject i at time t can be modeled as:

$$Y_{it} = \beta_0 + \mu_i + \alpha_i t + \beta_1 \cdot treatment + \beta_2 1_{[t=3]} + \beta_3 1_{[t=3]} \cdot treatment + \beta_4 1_{[t=5]} + \beta_5 1_{[t=5]} \cdot treatment + \beta_4 1_{[t=7]} + \beta_5 1_{[t=7]} \cdot treatment + \epsilon,$$

The error terms, ϵ , are assumed to be independent and normally distributed with constant variance and mean zero. If residual plots indicate that variance is not constant and/or the errors are not normally distributed,

transformations (e.g., the log transformation of the response) will be considered. Choice of covariance structures for the random effects (e.g., compound symmetric and autoregressive), will be explored.

In this model, the expected parasite load for the placebo group on Day 1 is β_0 , and on Day 3 ($t=3$) is $\beta_0 + \beta_2$. Therefore, the expected decrease from time Day 1 to Day 3 is β_2 for the placebo group. The expected parasite load for the treatment group on Day 1 is $\beta_0 + \beta_1$, and on Day 3, it is $\beta_0 + \beta_1 + \beta_2 + \beta_3$. Therefore, the expected decrease for the treatment group from Day 1 to Day 3 is $\beta_2 + \beta_3$. Thus, the difference in rate of decrease of parasite load from Day 1 to Day 3 between treatment and control groups is, on average, β_3 . The parameters β_5 and β_7 are interpreted analogously.

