4.4.2. Method of Assigning Subjects to Treatment Groups (Randomization)

Per International Conference on Harmonisation (ICH) guideline E6: Good Clinical Practice (GCP), screening records will be kept at the icddr, b site to document the reason why an individual was screened, but failed trial entry criteria. The reasons why individuals failed screening will be recorded in the Statistical and Data Coordinating Center's (SDCC) Advantage eClinical Electronic Data Capture System.

In the asymptomatic population, eligible subjects were stratified by disease strata (amebiasis or giardiasis), and then within each stratum, randomized 1:1 to receive auranofin or placebo. Enrollment was to continue in the other stratum after one stratum reached full enrollment. All subjects were to receive doses of the assigned medication or placebo delivered orally on Days 1, 2, 3, 4, 5, 6, and 7 for amebiasis and Days 1, 2, 3, 4, and 5 for giardiasis.

For the symptomatic population, randomization is stratified by site to prevent confounding that could arise from imbalance in treatment allocations between sites. Because the relative pace of enrollment between the two sites is unknown, the number of participants to be enrolled at each site is not fixed in advance. With this approach, the faster enrolling site may enroll more subjects, allowing enrollment to complete as quickly as possible. Each site may enroll up to 68 subjects into each stratum, so it is possible that one stratum could be filled entirely with subjects from a single site. With this flexible approach, treatment assignments may not be perfectly balanced (overall or within each site), but they will be approximately balanced. With sample sizes of 68 in each stratum, the impact of a small imbalance on power is negligible. Once eligibility and consent are confirmed, symptomatic subjects are stratified by site and infection (amebiasis or giardiasis), and then within each stratum, randomized 1:1 to receive auranofin or placebo. Enrollment will continue in the other arm after one arm reaches full enrollment. All subjects receive the assigned medication or placebo delivered orally on Days 1, 2, 3, 4, 5, 6, and 7 for amebiasis and Days 1, 2, 3, 4, and 5 for giardiasis.

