5. SAMPLE SIZE CONSIDERATIONS

The primary amebiasis outcome for this study is to compare the proportion of patients/subjects with resolution of diarrhea by Day 7 of therapy, in which placebo is expected to have a clearance rate of approximately 15-20%. Sample size calculations for both primary endpoints are based on a two-sample, two-sided binomial test for proportions, with alpha set to 0.05. Calculations were performed using the R statistical package (Version 3.0.2; <http://www.r-project.org>). The primary amebiasis endpoint in this aim is to compare the resolution of diarrhea between the two study arms to demonstrate that auranofin increases resolution of diarrhea. For this power analysis, we assume the following: a predicted diarrhea resolution rate of at least 80% (based on treatment results with current standard therapy with metronidazole [1]) in the auranofin treatment group.

With these assumptions, assuming 10% attrition (determined from the average of multiple other clinical trials in the same Mirpur district), a sample size of 68 with amebiasis (34 per arm; 60 completers in total) achieves greater than 95% power to detect a difference between the group proportions of 60%. The high statistical power for the primary endpoint is planned to also ensure adequate power for the secondary endpoints.

For the primary giardiasis endpoint of proportion of subjects with clearance of Giardia by Day 5, a similar sample size of 34 per arm will achieve 85% power to detect a 40% difference between treatment arms with a predicted clearance rate of 70% (based on response rates to metronidazole or tinidazole, Gardiner, 2001) and a 30% clearance rates in placebo.

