8. EFFICACY EVALUATION

All efficacy analyses will be performed on the modified Intention-to-Treat (mITT) population, as described in section 4.3.1, as a primary analysis. As a secondary analysis, the analysis will be repeated on the per-protocol population, as described in section 4.3.2. All tests will be two-sided and will use a significance level of 0.05. No adjustments will be made for multiple testing. All results will be reported as point estimates (differences in proportions, odds ratios or mean differences across groups, as appropriate) and interval estimates (95% confidence intervals).

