Note: These analyses will be performed both on the m-ITT population and the per-protocol population.
In the asymptomatic population, parasitological response is defined as no detection of cysts or trophozoites by microscopic exam or negative antigen detection.
Footnote 1: The method for CI calculation will be denoted here

Table 24: Comparison of Clearance Rates between Auranofin Group and Placebo Group, Symptomatic Amebiasis Group

		Clearance rate (proportion with parasitological response) by the specified day (95% CI)		
	Number of Subjects	Day 3	Day 5	Day 7
Auranofin, 6 mg				
Placebo				
Difference in clearance rates (95% CI)				

Note: These analyses will be performed both on the m-ITT population and the per-protocol population.
In the symptomatic population, parasitological response is defined as no detection of trophozoites by microscopic exam.
Footnote 1: The method for CI calculation will be denoted here.

Table 25: Comparison of Clearance Rates between Auranofin Group and Placebo Group, Symptomatic Giardiasis Group

		Clearance rate (proportion with parasitological response) by the specified day (95% CI)	
	Number of Subjects	Day 3	Day 5
Auranofin, 6 mg			
Placebo			
Difference in clearance rates (95% CI)			

Note: These analyses will be performed both on the m-ITT population and the per-protocol population.
In the symptomatic population, parasitological response is defined as no detection of trophozoites by microscopic exam.
Footnote 1: The method for CI calculation will be denoted here

Table 26: Mixed Effects Model Coefficient Estimates, Asymptomatic Amebiasis Group

Coefficient	Estimate	Standard Error	P-value
β_0 : Intercept			
β_1 : Treatment			
β_2 : Day 3			
β_3 : Day 3 * Treatment			
β_4 : Day 5			
β_5 : Day 5 * Treatment			
β_6 : Day 7			
β_7 : Day 7 * Treatment			

Note: These analyses will be performed both on the m-ITT population and the per-protocol population.

Table will be repeated for the symptomatic population

Table 27: Mixed Effects Model Coefficient Estimates, Asymptomatic Giardiasis Group

Coefficient	Estimate	Standard Error	P-value
β_0 : Intercept			
β_1 : Treatment			
β_2 : Day 3			
β_3 : Day 3 * Treatment			
β_4 : Day 5			
β_5 : Day 5 * Treatment			

Note: These analyses will be performed both on the m-ITT population and the per-protocol population.

Table will be repeated for the symptomatic population.

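### SAP 8.2.1 parasite-load model: a freely estimated Day 1 arm difference costs precision, and time form, scale and covariance are left open until the data by arm have been seen

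*SAP*

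**What the plan says.** SAP 8.2.1 models load on Days 1, 3, 5 and 7 with a random intercept and slope per subject. Section 8.2.2 carries the method over to giardiasis, where Table 27 stops at Day 5.

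- **Day 1.** In the day-by-day model the placebo mean on Day 1 is β₀. "The expected parasite load for the treatment group on Day 1 is" β₀ + β₁. In the linear model the Day 1 arm difference is β₂ + β₃ (the treatment term plus the treatment-by-time term at t = 1). Either way it is a free parameter, although subjects are "randomized 1:1 to receive auranofin or placebo" (SAP 4.4.2).
- **Time form and scale.** Mean load is plotted by day and treatment group. Use of the linear model then depends on what is seen: "If a linear relationship between parasite load and time is observed for both groups, then a model that makes use of this simplifying assumption". If the pattern is nonlinear, either a transformation may be applied or the day-by-day model is fitted. If residual plots look unsatisfactory, "transformations (e.g., the log transformation of the response) will be considered".
- **Covariance.** Structures for the random effects are to be explored. No order, criterion or blinded-review condition is given.
- **Reporting.** Table 26 in SAP Appendix 1 ("Mixed Effects Model Coefficient Estimates, Asymptomatic Amebiasis Group", repeated for the symptomatic population) has eight rows: intercept, treatment, each later day and each treatment-by-day term. Table 27 is the giardiasis counterpart. Neither has a row for a linear slope.
- **Testing.** SAP 8 states: "All tests will be two-sided and will use a significance level of 0.05". There is no multiplicity adjustment.

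The protocol's Final Analysis Plan (11.4) says only that mixed models with treatment-by-time terms will be considered. It gives the SAP precedence, so the SAP is where the detail has to be fixed.

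**The concern.** Randomization makes the pre-dose means of the arms equal in expectation. Estimating them separately discards that information, and the between-arm comparison then carries the full noise of the Day 1 measurement.

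The open choices matter for a different reason. A linear model tests one slope difference, while the day-by-day model gives an interaction per day with no test named as the comparison. A raw scale compares differences and a log scale compares ratios. Choosing among these after looking at means by arm makes the estimand depend on the data. The choice could also differ among the four population-by-disease groups in which the model is run. At stake are the precision and credibility of one secondary endpoint.

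**Working it through.** **The plan's own figures.** No SD, correlation, effect size or power is stated for load. The stated power concerns the primary endpoints: "Sample size calculations for both primary endpoints are based on a two-sample, two-sided binomial test for proportions, with alpha set to 0.05". For amebiasis, "a sample size of 68 with amebiasis (34 per arm; 60 completers in total) achieves greater than 95% power"; 80% against 20% at 30 per arm gives 99.8% by Fisher's exact test, so that holds. For giardiasis, 70% against 30% gives 83.8% at 30 per arm and 87.6% at 34, either side of the stated 85%. Neither figure depends on the load model.

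**Effect of the free Day 1 difference.** Let r be the correlation of Day 1 load with a later load, k the later SD divided by the Day 1 SD, and n the number per arm. In units of (2/n) × the Day 1 variance, with complete data and known covariance:

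- separate Day 1 means (change score): k² − 2rk + 1
- common Day 1 mean (baseline-adjusted): k²(1 − r²)
- difference: (kr − 1)², which is never negative and is zero when kr = 1

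The ratio of the second to the first does not depend on n. Under equal variances (k = 1) it is (1 − r²)/(2 − 2r) = (1 + r)/2:

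| r (assumed) | variance ratio | SE excess of SAP model |
|---|---|---|
| 0.2 | 0.60 | 29% |
| 0.3 | 0.65 | 24% |
| 0.5 | 0.75 | 15% |
| 0.7 | 0.85 | 8% |
| 0.9 | 0.95 | 3% |

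With unequal variances at r = 0.5:

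- k = 1.5: 2.25 × 0.75 / (2.25 − 1.5 + 1) = 1.6875/1.75 = 0.96
- k = 2: 4 × 0.75 / (4 − 2 + 1) = 3/3 = 1.00, no gain

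With a random intercept (variance 1), an independent random slope per day from Day 1, and residual error, all illustrative, the covariance of Days 1 and 7 is 1:

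| slope var. | residual var. | Day 1 var. | Day 7 var. | change | adjusted | ratio |
|---|---|---|---|---|---|---|
| 0.02 | 1 | 2 | 2.72 | 2.72 | 2.22 | 0.82 |
| 0.05 | 0.7 | 1.7 | 3.5 | 3.2 | 2.91 | 0.91 |
| 0.1 | 1 | 2 | 5.6 | 5.6 | 5.1 | 0.91 |
| 0.2 | 0.7 | 1.7 | 8.9 | 8.6 | 8.31 | 0.97 |

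Here the SAP model's SE is about 2% to 11% larger. A simulation of 20,000 trials (34 per arm, random intercept and slope, r = 0.50) gave 0.77. The formula gives that value at r = 0.5 when k is about 1.03, so it represents nearly equal variances.

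As an illustration in power, take an assumed effect of 0.75 SD, r = 0.5, equal variances and 30 per arm. The SEs are √(2/30) = 0.258 and √(1.5/30) = 0.224, and power is 83% against 92%.

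**Effect of the open form.** In a null simulation (10,000 trials, 30 per arm, log-normal loads, r = 0.5, log SD 1 or 2), four analyses were run: slope or Day 7 change, on the raw or log scale. Each alone rejected in 2% to 5% of trials; at least one of the four rejected in 8% to 10%. Adding the Day 3 and Day 5 changes raised this to 16% to 17%. These are ceilings that apply only if the analysis is picked for its result.

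**The printed subscripts.** The day-by-day equation shows β₄ and β₅ for both Day 5 and Day 7. The explanatory paragraph below it refers to β₇, and Table 26 lists β₆ and β₇ for Day 7. Read literally, true effects of −1 on Day 5 and −2 on Day 7 would both return −1.5, with a smaller SE (0.224 against 0.258 at r = 0.5).

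**The case against.** A difference in change from Day 1 is a standard, unbiased answer to an objective worded as rate of decrease, so the free Day 1 term is not an error. That stands; the point is efficiency only.

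The size of the gain is not in the documents. That also stands. Because (1+r)/2 needs equal variances and the SAP specifies a random slope, later-day variance may well exceed Day 1 variance, and the gain may then be small.

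SAP 8.2.1 presents the model first for the per-protocol analysis. That population is selected after randomization, by adherence, by sampling windows and by case-by-case removal (SAP 6.3.2), so randomization does not guarantee a common Day 1 mean there. This limits the proposal to mITT. The mITT exclusions (SAP 6.3.1 and 6.3.1.1) rest on no dose having been dispensed and on status at enrolment, so the argument carries over there if dispensing is unrelated to arm.

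Tables 26 and 27 already imply categorical days. That narrows the open choices but does not remove them: the linear sentence contradicts the tables, and scale and covariance stay open. SAP 15 shows that the transformation option was added deliberately, for better fit. A wish for good fit is reasonable, but it does not require choosing after viewing means by arm.

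Fixing log10 load alone would be incomplete. Protocol 8.2.1, Appendix B and SAP 4.5.1 run quantitative PCR on positive stools, and no value is given for a negative stool. This stands and is added to the fix.

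**Conclusion.** The point holds as one of efficiency and pre-specification for a secondary endpoint. The separate Day 1 means give an unbiased comparison that is never more precise than the baseline-adjusted one when the covariance is known, and is usually less precise. The variance ratio runs from 0.60 to 0.95 for r from 0.2 to 0.9 under equal variances and from about 0.77 to 0.97 in the random-slope illustrations. It is near 1 when kr is near 1. All of these rest on assumed correlations and variances.

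Four stronger readings are tempting but unsupported:

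- That the model wastes the equivalent of a third more subjects. That is 1/0.75 = 1.33, which needs r = 0.5 and equal variances; the documents give neither.
- That the type I error will be 8% to 10%. Nothing in the SAP says the form will be picked for its treatment effect, so this is a ceiling.
- That Day 7 will not be estimated separately. The mention of β₇ and the eight rows of Table 26 settle the intended model. The repeated subscripts are clerical, possibly an artefact of text extraction, and do not arise for giardiasis.
- That the primary result or sample size is affected. Neither uses this model.

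**What to change.** Amend SAP 8.2.1, and 8.2.2 by reference:

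1. Delete the linear alternative. Use categorical days (1, 3, 5, 7 for amebiasis; 1, 3, 5 for giardiasis), as Tables 26 and 27 already report.
2. Fix log10 load as the scale and state the value or censoring rule for negative stools.
3. In the mITT analysis, omit the treatment main effect at Day 1, so that the arms share one baseline mean, using pre-dose samples only. First reconcile the sampling text: Protocol Appendix B says the Day 1 DNA comes from stool obtained before the first dose, while Protocol 7.2, Appendix A and the same row of Appendix B allow a window of +1 day. In the per-protocol analysis, do not justify a common Day 1 mean by randomization.
4. Name one covariance structure with a fallback if it fails to converge, and one between-arm test.
5. Relabel the Day 7 terms β₆ and β₇ as an editorial correction.

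The treatment row of Table 26 and Table 27 drops out for the mITT version. The cost is SAP wording, one model statement and a small edit to two table shells; no new data are needed.

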3.2.2. Symptomatic Population Endpoints

Primary Outcome Measures

1. Proportion of subjects with positive rapid EIA and positive antigen detection EIA for *E. histolytica* and resolution of diarrhea (less than 3 loose stools/ 24 hours) by Day 7.
2. Proportion of subjects with positive rapid EIA and positive antigen detection EIA for *Giardia* and resolution of diarrhea (less than 3 loose stools/24 hours) by Day 5.

Secondary Outcome Measures

1. *E. histolytica*:

- a. Proportion of subjects with positive rapid EIA and positive antigen detection EIA for *E. histolytica* and trophozoites on smear at enrollment with parasitological response (no detection of trophozoites on microscopic exam) by Day 7.
- b. Proportion of subjects with positive rapid EIA and positive antigen detection EIA for *E. histolytica* and trophozoites on smear at enrollment with parasitological response (no detection of trophozoites on microscopic exam) by Day 3 and 5.
- c. Rate of decrease of trophozoite/cyst load by qPCR in stools by Days 3, 5, and 7
- d. Proportion of subjects with negative stool antigen test by Days 3, 5, 7, and 14
- e. Proportion of subjects with sustained cure (no detection of trophozoites by microscopic exam) at 14 and 28 days
- f. Proportion of subjects with relapse (same strain) or re-infection (new strain) with positive stools at 14 and 28 days by genotyping the initial vs. subsequent strain
- g. Time to resolution of diarrhea (less than 3 loose stools/24 hours)

2. *Giardia*:

- a. Proportion of subjects with positive rapid EIA and positive antigen detection EIA for *Giardia* and trophozoites on smear at enrollment with parasitological response (no detection of trophozoites on microscopic exam) by Day 3 and 5
- b. Rate of decrease of trophozoite/cyst load by qPCR in stools by Days 3 and 5
- c. Proportion of subjects with negative stool antigens by days 3 and 5.
- d. Proportion of subjects with sustained cure (no detection of trophozoites by microscopic exam) at 14 and 28 days
- e. Proportion of subjects with relapse (same strain) or re-infection (new strain) with positive stools at 14 and 28 days by genotyping the initial vs. subsequent strain
- f. Time to resolution of diarrhea (less than 3 loose stools/24 hours)

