The secondary outcomes will be summarized in [Table 22](#) through [Table 34](#). [Table 22](#) and [Table 24](#) will present clearance rates for the amebiasis group with 95% confidence intervals on Days 3, 5, and 7 for the treatment and placebo groups, as well as the differences in clearance rates and 95% confidence intervals for the differences. [Table 23](#) and [Table 25](#) are analogous tables for the giardiasis group. [Table 26](#) will present the coefficient estimates for the mixed effects model for the amebiasis group. [Table 27](#) is the analogous table for the giardiasis group. [Table 28](#) will present the proportion of subjects in the amebiasis group with negative stool antigen test on Days 1, 3, 5, 7, and 14. This outcome is not analyzed for the giardiasis group. [Table 29](#) will present the proportion of subjects with sustained cure for the amebiasis group on days 7, 14, and 28, for each treatment arm, with 95% confidence intervals, as well as the difference in proportions between treatment arms and 95% confidence interval for the difference. [Table 30](#) will present analogous summaries for the giardiasis group (Day 5 instead of Day 7). [Table 31](#) will present the proportion of subjects in the amebiasis group with relapse by Day 14, the proportion with reinfection by Day 14, and the proportion with either relapse or reinfection by Day 14, separately for each treatment arm, with 95% confidence intervals. [Table 32](#) is the analogous table for the giardiasis group. Differences in proportions between treatment arms and 95% confidence intervals for the differences will also be included. [Table 33](#) will present a perfectly analogous summary for Day 28 rather than Day 14, for the amebiasis group. [Table 34](#) is the analogous table for the giardiasis group. [Listing 15](#) and [Listing 16](#) provide a listing for all efficacy endpoints for the amebiasis groups; [Listing 17](#) and [Listing 18](#) are the analogous listings for the giardiasis groups.

The secondary outcomes for the symptomatic population are identical to those for the asymptomatic population with the following exceptions:

- Parasitological response is defined differently, and parasitological response on Day 5 (giardiasis) and Day 7 (amebiasis) were changed from primary to secondary.
- Time to resolution of diarrhea was added as an endpoint.

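### SAP 8.2.1 calls signed changes in parasite load a decrease, so the stated key to the treatment contrast has the wrong sign; in the day-indicator model the contrasts are also totals, not rates

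*SAP*

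**What the plan says.** The endpoint for symptomatic amebiasis is "Rate of decrease of trophozoite/cyst load by qPCR in stools by Days 3, 5, and 7" (SAP 3.2.2). The asymptomatic amebiasis group has the same endpoint, and the giardiasis groups have it for Days 3 and 5.

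SAP 8.2.1 offers two mixed models for it. The first is linear in study day and is used if the plotted means look linear in both arms. Otherwise the response may be transformed, or a second model with an indicator for each follow-up day is fitted. The outcome is the load: "Letting Y denote parasite load, t denote the time point (study day), and i be a subject index". Treatment is coded 1 for auranofin and 0 for placebo. For the random intercept and slope the SAP says to "assume these random effects are normally distributed with mean zero".

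The SAP then interprets the indicator model. "In this model, the expected parasite load for the placebo group on Day 1 is" β0, and on Day 3 it is β0+β2; the auranofin means are β0+β1 and β0+β1+β2+β3. From these it names β2 as the placebo decrease and continues: "Therefore, the expected decrease for the treatment group from Day 1 to Day 3 is" β2+β3. It concludes that "the difference in rate of decrease of parasite load from Day 1 to Day 3 between treatment and control groups is, on average" β3, with β5 and β7 to be read in the same manner.

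Table 26 "will present the coefficient estimates for the mixed effects model for the amebiasis group", and Table 27 does the same for giardiasis. Both shells list coefficients by day and by day-times-treatment, with a standard error and a p-value. They have no contrast row, no confidence interval and no note on direction.

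**The concern.** When the outcome is a load, a fall gives a negative time coefficient, and a faster fall on auranofin gives a negative interaction. The SAP's sentence calls that negative number a difference in decrease. A report writer who applies it as written to a negative β3 would say that auranofin cleared parasites more slowly than placebo.

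A second issue is independent of the first. The endpoint is a rate, but each interaction in the indicator model covers a different length of time. Reading all three in the same manner as rates would make a constant daily advantage look as if it grew from visit to visit.

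Parasite load is the only parasitological outcome on a numeric scale, and Tables 26 and 27 are to be produced for both study populations and for both the modified intention-to-treat and per-protocol sets. Any misreading would therefore be repeated several times.

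**Working it through.** **Inputs (SAP 8.2.1).** Y is load; auranofin = 1 and placebo = 0; the random effects have mean zero and drop out of the expected values. Measurements are on Days 1, 3, 5 and 7, so the intervals from Day 1 are 2, 4 and 6 days.

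**1. Reproducing the SAP's expressions.** They come out if change is taken as Day 3 minus Day 1:

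- placebo: (β0+β2) − β0 = β2
- auranofin: (β0+β1+β2+β3) − (β0+β1) = β2+β3
- auranofin minus placebo: β3

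**2. The same quantities as decreases.** A decrease is Day 1 minus Day 3:

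- placebo: β0 − (β0+β2) = −β2
- auranofin: (β0+β1) − (β0+β1+β2+β3) = −(β2+β3)
- auranofin minus placebo: −(β2+β3) + β2 = −β3

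The SAP's three expressions are therefore correct as changes and have the opposite sign as decreases. The same holds for the Day 5 and Day 7 contrasts, −β5 and −β7 (numbered as in Table 26).

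**3. Illustration.** The documents give no loads, so these log10 means are assumed: placebo 6.0, 5.0, 4.4, 4.0 and auranofin 6.1, 4.1, 2.9, 2.5 on Days 1, 3, 5 and 7.

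| Interval | Interaction | Extra decrease on auranofin | Days | Per day |
|---|---|---|---|---|
| Day 1–3 | β3 = (4.1−6.1) − (5.0−6.0) = −1.0 | 1.0 | 2 | 0.50 |
| Day 1–5 | β5 = (2.9−6.1) − (4.4−6.0) = −1.6 | 1.6 | 4 | 0.40 |
| Day 1–7 | β7 = (2.5−6.1) − (4.0−6.0) = −1.6 | 1.6 | 6 | 0.27 |

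To Day 3, placebo falls by 1.0 and auranofin by 2.0. The SAP's wording would give decreases of −1.0 and −2.0 and a difference of −1.0. A simulated fit of the indicator model to 2,000 subjects with these means returned β2 = −0.98 and β3 = −1.01. The software warned of a possible boundary estimate, and the algebra does not depend on the fit.

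**4. Scale.** Suppose the slopes differ by a constant −0.2 per day. Then β3 = −0.2×2 = −0.4, β5 = −0.2×4 = −0.8 and β7 = −0.2×6 = −1.2. The difference in rate of decrease is 0.2 per day throughout, yet the three coefficients differ by a factor of up to three.

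**5. Linear model.** Here the mean slope is β1 on placebo and β1+β3 on auranofin. β3 is already a difference per day, and it is negative when auranofin falls faster. The scale point does not arise.

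**6. Printed equation.** The Day 7 terms of the indicator model reuse β4 and β5, so the β7 that the text interprets does not appear in it. Table 26 numbers these terms β6 and β7. This is probably a typing slip.

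**The case against.** The strongest reply is that no planned output carries the faulty wording. Tables 26 and 27 print raw coefficients under neutral labels. The same section states the model's aim as comparing arms on rate of change, and for change β3 has the right sign. The estimate, its standard error and the two-sided p-value do not depend on what the coefficient is called. The section also requires mean load with 95% confidence intervals to be plotted by arm and day, and Listings 15 to 18 give load by subject and day. With two falling curves in view and decreases of −1.0 and −2.0 on the page, most analysts would see that the numbers are signed changes.

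All of that stands, and it rules out several stronger readings that a reader might infer:

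- That a benefit of auranofin will be reported as harm. This follows only if one sentence is applied literally and the graph is ignored.
- That the paragraph is the only guide to direction. The graph, the listings and the correctly stated expected loads are others.
- That the scale problem contributes to the reversal. Both arms are divided by the same number of days, so direction cannot change.
- That the scale problem affects both models. It does not affect the linear one, although the table shells are laid out only for the indicator form.

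What the reply does not remove is that the SAP's only written statement of what the treatment contrast means gives the opposite direction when taken at its word.

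**Conclusion.** The point holds as a wrong interpretation rule, with limited consequences. In the indicator model the auranofin-minus-placebo difference in decrease is −β3, −β5 and −β7, not β3, β5 and β7; this is algebra on the SAP's own means and needs no outside figure. Also, and independently, those contrasts are totals over 2, 4 and 6 days, although the endpoint is a rate.

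Taken literally, the sign error is complete: the size is right and the direction is opposite. The scale error is a factor of 2, 4 or 6 relative to an average daily rate. The numerical illustrations rest on assumed log10 loads. The documents do not support a claim that any estimate or test would be wrong, and the primary analyses do not use this model. The text should be corrected before the tables are produced.

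**What to change.** In SAP 8.2.1, either replace the word decrease with change from Day 1, or define the expected decreases as −β2 and −(β2+β3) and the differences in decrease as −β3, −β5 and −β7. When the indicator model is used, divide these by 2, 4 and 6 to obtain average daily rates. When the linear model is used, −β3 is already the daily difference and needs no division.

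State that a negative interaction favours auranofin. If the response is log-transformed, say that the contrast is a log ratio; on the log10 scale, for example, −β3 = 1.0 would mean a 10^1.0 = 10-fold greater reduction.

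Add the contrasts to Table 26 (Days 3, 5 and 7) and Table 27 (Days 3 and 5) and their symptomatic repeats, with the 95% confidence intervals that SAP section 8 already promises for all results. Renumber the Day 7 terms of the printed equation as β6 and β7 to match Table 26.

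The cost is a few lines of SAP text, three derived rows in Table 26 and two in Table 27. No new data are needed, and the model and tests are unchanged.
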